## 5. STUDY TREATMENTS

For the purposes of this study, and per International Conference on Harmonisation (ICH) guidelines, investigational product is defined as a pharmaceutical form of an active ingredient or placebo being tested or used as a reference in a clinical trial, including a product with a marketing authorization when used or assembled (formulated or packaged) in a way different from the approved form, or when used for an unapproved indication, or when used to gain further information about an approved use (ICH E6 1.33).

In this study, the investigational products are all study treatments to be administered, namely, avelumab (MSB0010718C)/placebo and SOC CRT. The study treatments include the following:

- Arm A: Avelumab + SOC CRT:
  - Avelumab 10 mg/kg IV: Day 1 of the Lead-in phase; Days 8, 25, and 39 of the CRT Phase; Q2W for 12 months during the Maintenance Phase.
  - Cisplatin 100 mg/m^2 IV: Days 1, 22, and 43 of the CRT Phase.
  - IMRT 70 Gy/35 fractions/7 weeks; 1 fraction/day, 5 fractions/week for 7 weeks during the CRT Phase.
- Arm B: Placebo + SOC CRT:
  - Placebo IV matching avelumab: Days 1 of the Lead-in phase; Days 8, 25, and 39 of the CRT Phase; Q2W for 12 months during the Maintenance Phase.
  - Cisplatin 100 mg/m^2 IV: Days 1, 22, and 43 of the CRT Phase.
  - IMRT 70 Gy/35 fractions/7 weeks; 1 fraction/day, 5 fractions/week for 7 weeks during the CRT Phase.

Note: The Day 25 dose of avelumab/placebo during the CRT Phase may be administered between Day 24 and Day 29.

### **5.1. Allocation to Treatment**

Patients will be randomized in a 1:1 ratio to either Arm A (avelumab + SOC CRT) or Arm B (placebo + SOC CRT). Randomization will be stratified by tumor stage (<T4 vs T4), nodal stage (N0/N1/N2a/N2b vs N2c/N3), and HPV status (positive vs negative) measured by p16 expression by IHC.

Assignment of patient number, patient enrollment, and allocation of study drug will be managed by the Interactive Response Technology (IRT) system (interactive web-based response [IWR]). At the time that a patient has signed informed consent and entered screening, the site should contact the IRT system to obtain the patient identification number. Once a patient has met all eligibility criteria, the site then contacts the IRT system to enroll the patient and to obtain the study drug allocation information. Study treatment must be initiated preferably on the day of randomization, but no later than 3 days after randomization.

At the time of enrollment, site personnel (study coordinator or specified designee) will be required to enter into or select information from the IRT system including but not limited to the user's identification (ID) and password, the protocol number, the patient number, and the date of birth of the patient. The IRT system will then provide a treatment assignment (Arm A or Arm B) and dispensable unit (DU) or vial number. The IRT system will also provide a confirmation report containing the patient number and DU or vial number assigned. The confirmation report must be stored in the site's files.

There is a 24-hour-a-day, 365-days-a-year IRT helpdesk available for any questions or issues. The study-specific IRT reference manual will provide the contact information and further details on the use of the IRT system.

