### **5.2. Breaking the Blind**

At all times, treatment and randomization information will be kept confidential and will not be released to the patient, investigator, the study staff, or the sponsor's study team until following the conclusion of the study, with the exception described in this section.

At the initiation of the study, the study site will be instructed on procedures for breaking the blind. Blinding codes should be broken only in emergency situations for reasons of patient safety. If a patient has an adverse event (AE) that may be considered immune mediated, treatment for the AE should be administered as if the patient is receiving avelumab. Whenever possible, the investigator should contact Pfizer before breaking the blind. The method will be either a manual or electronic process. When the blind for a patient has been broken, the reason must be fully documented. If the blind is broken, the investigator should promptly inform the Pfizer Clinician or Medical Monitor. The patient for whom the blind has been broken will be discontinued from the study treatment and undergo the post-treatment (End-of-Treatment [EOT]/Follow-up) procedures.

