### **5.4.3. Avelumab/Placebo**

#### **5.4.3.1. Dosage Form and Packaging**

Avelumab/placebo will be supplied for the study by Pfizer Global Clinical Supply, Worldwide Research and Development. Drug supplies will be shipped to the study sites with a Drug Shipment and Proof of Receipt form. This form will be completed, filed, and the shipment confirmed as directed on the bottom of the Drug Shipment and Proof of Receipt form. The Investigator shall take responsibility for and shall take all steps to maintain appropriate records and ensure appropriate supply, storage, handling, distribution, and usage of investigational products in accordance with the protocol and any applicable laws and regulations.

Avelumab is a sterile, clear, and colorless solution intended for IV administration. It is presented at a concentration of 20 mg/mL with a nominal volume of 10 mL in glass vials closed with a rubber stopper and sealed with an aluminum polypropylene flip-off seal. Each vial is intended for single-use only.

The placebo for avelumab is a sterile, clear, and colorless solution for IV administration presented with a nominal volume of 10 mL in matching glass vials. Each vial is intended for single-use only.

Packaging and labeling of avelumab/placebo will be blinded to all investigative personnel in accordance with applicable local regulatory requirements and applicable Good Manufacturing Practice (GMP) guidelines. Avelumab/placebo will be packed in boxes each containing one vial. The information on the trial drug will be in accordance with approved submission documents.

Avelumab/placebo will be shipped in transport cool containers (2°C to 8°C) with temperature monitoring devices.

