### **7.1. Assessment of Progression**

For all suspected progression of disease that is detected clinically, but is not visible on radiographic imaging, direct imaging (ie, photographs) are required. This requirement is in addition to the requirement for pathologic confirmation of progression.

Tissue (pathologic) confirmation of disease is expected and required on this protocol for all local and regional lymph node suspected progression of disease. It is highly recommended that all new distant lesions suspicious for metastatic disease are also biopsied and pathologically confirmed. Good clinical judgment is expected to be utilized on biopsy ascertainment including, but not limited to, the situations below.

The following are expectations for biopsy ascertainment on a patient. If any of these conditions are met, it is expected that a biopsy will be performed, and the reason for biopsy and pathologic findings noted in the CRF. If a biopsy is not performed, clinical rationale must be entered into the CRF.

- New or significantly increased lesions on imaging or clinical exam;
- Mucosal ulceration;
- Suspicious mucosal changes;
- Suspicion of unresolved disease at the primary tumor location at the 12 week post CRT visit (primary treatment failure and a PD event if biopsy is positive);
- Significant enlargement, or newly enlarged, regional lymph nodes on clinical exam or imaging;
- Areas of PET-positive fludeoxyglucose (FDG)- uptake;
- Change of clinical findings on regional lymph node (neck) exam with new enlargement of a lymph node or group of nodes, or changes in character of lymph node group to palpation (eg, becoming harder or decreased mobility on physical exam - such as feeling attached to overlying skin, subcutaneous tissue or muscles, or underlying bone or muscle).

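### Protocol Section 5.1 has the IRT give site staff the treatment arm, which contradicts the blinding rules in Sections 5.2 and 5.4.3.1

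*Protocol*

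**What the plan says.** Protocol Section 5.1 (Allocation to Treatment) describes enrolment in three steps. Once eligibility is met, "the site then contacts the IRT system to enroll the patient and to obtain the study drug allocation information". At that point "site personnel (study coordinator or specified designee) will be required to enter into or select information from the IRT system". Then "The IRT system will then provide a treatment assignment (Arm A or Arm B) and dispensable unit (DU) or vial number". The arm and the vial number are listed as two separate outputs. The following sentence describes a confirmation report that holds the patient number and the assigned unit or vial number; it does not mention an arm.

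The labels are defined in the first sentence of the same section: "Patients will be randomized in a 1:1 ratio to either Arm A (avelumab + SOC CRT) or Arm B (placebo + SOC CRT"). Section 5 (Study Treatments) repeats the definition: "Arm A: Avelumab + SOC CRT".

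Two other sections point the opposite way. Section 5.2 (Breaking the Blind) gives this rule: "At all times, treatment and randomization information will be kept confidential and will not be released to the patient, investigator, the study staff". Its stated exception is an emergency code break for patient safety. Section 5.4.3.1 (Dosage Form and Packaging) adds: "Packaging and labeling of avelumab/placebo will be blinded to all investigative personnel".

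The primary endpoint is PFS per modified RECIST v1.1 by investigator assessment (Protocol Section 2.2, SAP Section 3.1). PFS by blinded independent central review appears in SAP Section 6.2.2.2 as analyses S0_B and M1_B. Both use standard RECIST v1.1, and both fall under that section's description of the sensitivity analyses as exploratory.

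**The concern.** A site that follows Section 5.1 to the letter learns which patients receive avelumab, and a site that follows Section 5.2 may not. One of the two instructions must give way, and the text does not say which.

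The trial relies on the blind at several points. Whether a suspicious lesion is biopsied, and whether a finding is called progression, rest partly with the investigator; Section 7.1 says "Good clinical judgment is expected to be utilized on biopsy ascertainment". Locoregional progression counts only with pathology, so a lesion that is never biopsied is not a locoregional event. Distant progression can be called without a biopsy. Adverse-event causality is judged separately for each drug (Section 8.9), the patient-reported outcomes are self-reported, and Appendix 4 gives the double-blind design as a reason for not requiring confirmation of response. Knowledge of the arm could influence each of these.

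**Working it through.** This is mainly a comparison of texts. The claim has five links.

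1. **Who receives the IRT output?** The site, through a study coordinator or designee (Section 5.1).
2. **Does the output include the arm?** Yes, named separately from the vial number (Section 5.1).
3. **Is the arm label a masked code?** No. Sections 3.1, 5 and 5.1 all define Arm A as the avelumab arm and Arm B as the placebo arm.
4. **Is any site role allowed to hold unblinded information?** None is described. Section 9.3.2.9 places the central and analytical laboratories and the sponsor's assay group outside the blind. Section 9.7 and SAP Section 7.1 do the same for the data monitoring committee and the independent statistician. There is no unblinded site pharmacist and no stated separation between the person using the IRT and the assessing investigator. The direct recipient is the coordinator or designee; the investigator's exposure follows from that missing separation.
5. **Does this conflict with another rule?** Yes. Section 5.2 covers both the investigator and the study staff, and Section 5.4.3.1 covers all investigative personnel.

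The blinded vial number is sufficient for dispensing, so the arm serves no purpose in the site's output.

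**What knowledge of the arm could and could not change.** It could affect whether a lesion is biopsied and whether a finding is called progression. It would not shift a radiographic locoregional progression through a later confirmatory biopsy, because that event is dated to the scan (Protocol Section 7.8, SAP Section 6.1.1.1). It would not remove deaths, which are PFS events in their own right.

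**Illustration only.** Inputs: 289 PFS events at the final analysis, 1:1 allocation, and the final one-sided criterion p < 0.022 when the interim falls at exactly 217 events (SAP Section 5.1.2). The critical value is Φ⁻¹(0.022) = −2.014. The expected log-rank statistic is approximately (√289 / 2) × ln(HR) = 8.5 × ln(HR). Assume no true effect and a recorded Arm A hazard lowered by 5%, 10% or 15%:

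| Recorded HR | 8.5 × ln(HR) | P(z < −2.014) |
|---|---|---|
| 1.00 | 0 | 0.022 |
| 0.95 | −0.436 | 0.057 |
| 0.90 | −0.896 | 0.132 |
| 0.85 | −1.381 | 0.263 |

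The three reductions are assumptions with no source in the documents, and they are applied to all 289 events, deaths included. If a share d of events are deaths without prior progression, an overall reduction r requires the progression component to fall by about r / (1 − d). The documents do not give d. The table covers the final criterion alone and ignores the interim look.

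**The case against.** The strongest reply is that one sentence is being set against a protocol otherwise written for blinded sites. Placebo vials match. Section 5.2 has possible immune-mediated events managed as though the patient were on avelumab, and it prescribes a formal code-break procedure with consequences; neither would make sense if sites already held the arm. The confirmation report is described without an arm. Section 5.1 refers to a study-specific IRT manual, which is not among the documents, so what users actually see is unknown. The natural reading is a drafting slip. This stands, and it limits the finding to a contradiction in the text.

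The plan also constrains and monitors investigator judgement. Assessments follow the same schedule in both arms. Section 7.1 lists situations in which a biopsy is expected and requires a reason in the CRF when none is done. SAP Section 6.2.2.2 adds the central-review analyses, discordance rates by arm, and a by-arm summary of biopsies done and not done with reasons. That summary could reveal differential biopsy behaviour. These measures are real, but they detect a problem after the fact and do not protect the primary test. The central review also uses a different progression definition and cannot supply pathology from a biopsy that was never taken.

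Three stronger readings are tempting, and the documents do not support them:

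- That sites were in fact unblinded. The text shows conflicting instructions and no such event.
- That investigator judgement determines most of PFS. Deaths count, locoregional events need pathology, and nothing in the documents gives the mix of events.
- That the false-positive rate is 6% to 26%. Those figures show what a bias of the assumed size would do to a log-rank test of 289 events. They do not estimate the effect of this sentence.

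**Conclusion.** Section 5.1 is wrong as written. It gives site staff a label that identifies the treatment, and it cannot be followed together with Sections 5.2 and 5.4.3.1. Confidence in that contradiction is high, because every element stands in the current protocol and no other text resolves it.

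The practical consequence is conditional. If the IRT was built to agree with Section 5.2, the error is confined to the protocol text. If it was built as Section 5.1 says, the masking of up to approximately 640 patients is in question, in a trial whose primary endpoint is investigator-assessed. The documents cannot tell which applies, and the size of any bias cannot be derived from them. The point needs correction because two mandatory instructions conflict on the blind behind the primary analysis.

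**What to change.** Reword the sentence in Section 5.1 so that the IRT returns a randomization confirmation and the blinded dispensable unit or vial number, and state that the treatment arm is not displayed or reported to any site user.

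Check the IRT specification, the user screens and the IRT reference manual for agreement with Section 5.2, and keep a record of the check. It is worth doing even if randomization has finished, because it is the evidence behind the double-blind description.

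Only if the check shows that an arm was displayed, record the affected patients as unblinding deviations. The sponsor would then also have to reconcile that situation with the consequences Section 5.2 attaches to a broken blind; no clinical rule is proposed here.

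The cost is one sentence in an amendment plus a configuration and document check. No extra patients, visits or procedures are needed.

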### **5.2. Breaking the Blind**

At all times, treatment and randomization information will be kept confidential and will not be released to the patient, investigator, the study staff, or the sponsor's study team until following the conclusion of the study, with the exception described in this section.

At the initiation of the study, the study site will be instructed on procedures for breaking the blind. Blinding codes should be broken only in emergency situations for reasons of patient safety. If a patient has an adverse event (AE) that may be considered immune mediated, treatment for the AE should be administered as if the patient is receiving avelumab. Whenever possible, the investigator should contact Pfizer before breaking the blind. The method will be either a manual or electronic process. When the blind for a patient has been broken, the reason must be fully documented. If the blind is broken, the investigator should promptly inform the Pfizer Clinician or Medical Monitor. The patient for whom the blind has been broken will be discontinued from the study treatment and undergo the post-treatment (End-of-Treatment [EOT]/Follow-up) procedures.

### **5.3. Patient Compliance**

All doses of study treatments (avelumab or placebo and SOC CRT) will be administered at the investigational site by well-trained medical staff.

The information related to each trial drug administration, including the date, time, and dose of study drug, will be recorded on the electronic case report form (eCRF). The Investigator will make sure that the information entered into the eCRF regarding drug administration is accurate for each patient. Any reason for noncompliance should be documented.

Noncompliance is defined as a patient missing >1 infusion of any study treatment (avelumab/placebo or cisplatin) for non-medical reasons. If 1 infusion is missed and the interval between the subsequent infusion and the last administered treatment is longer than 4 weeks for nonmedical reasons, the criteria of insufficient compliance will have been met as well. Non-compliance with radiation is defined in the Radiation Delivery Guidelines Document.

### **5.4. Investigational Product/Study Treatments Supplies**

#### **5.4.1. Radiation Therapy to the Primary Lesion and Neck (IMRT)**

##### **5.4.1.1. Dose Specifications**

Radiation therapy (RT) will be delivered using IMRT technique and will be delivered in 35 fractions over 7 weeks, 5 fractions weekly either in one plan (simultaneous integrated boost [SIB]) or through separate plans, of cone-down boosts. Detailed definitions of clinical target volumes to encompass gross disease with appropriate margin (clinical target volume [CTV]1), high risk sub-clinical disease sites (CTV2) and lower risk areas, as well as normal tissue maximal doses are detailed separately in the Radiation Delivery Guidelines Document.

For questions regarding IMRT, please contact [name] [REDACTED] or call PPD [REDACTED].

##### **5.4.1.2. Technical Factors**

###### **5.4.1.2.1. Treatment Planning/Delivery**

Megavoltage energy photon beam irradiation is required. Any treatment planning and delivery system that has been credentialed for head and neck IMRT for cooperative group radiation studies (eg, NRG Oncology, Radiation Therapy Oncology Group [RTOG], or EORT) is acceptable. See Radiation Delivery Guidelines Document for additional details.

###### **5.4.1.2.2. Localization, Simulation, and Immobilization**

Patients must have an immobilization device (eg, Aquaplast mask) made prior to treatment planning CT scan.

Although not mandatory, the treatment planning CT scan should be performed with IV contrast so that the major vessels of the neck are easily visualized. However, when possible, fusion of respective diagnostic imaging such as PET/CT and/or MRI should be done to carefully delineate the gross tumor volume. The treatment planning CT scan must be

performed with the immobilization device and in the treatment position. Slice thickness should be 0.3 cm or less.

#### **5.4.1.3. Documentation Requirements for IMRT**

Documentation requirements for IMRT are described in the Radiation Delivery Guidelines Document and include the following:

- Pre-treatment radiation therapy planning CT scan;
- All radiation treatment plans will undergo full, centralized, real-time quality assurance (QA), consisting of a rapid review prior to IMRT initiation and a full review of the delivered plan at the completion of therapy. Details of the IMRT review and treatment plan submission process will be provided in the Radiation Delivery Guidelines Document;
- All treatment plans are to be normalized to provide exactly 95% volume coverage of the PTV1 with 70 Gy.

#### **5.4.1.4. Compliance Criteria**

Treatment breaks must be clearly indicated in the treatment record along with the reason(s) for the treatment break(s). Treatment breaks are highly discouraged; however, if necessary for severe acute toxicity, ideally should not exceed 5 treatment days at a time and 10 treatment days in total. Treatment breaks should be allowed only for resolution of severe acute toxicity and/or for intercurrent illness.

Days that the RT department is closed, RT is not expected to be administered and this is not a treatment break. This includes all statutory holidays in that locale. Over times of multiple, consecutive days of holidays, the site is encouraged but not required to “make up” the RT fractions through BID treatments, at least 6 hours apart, during the shortened treatment week.

It is recognized that over the course of 35 treatment fractions in RT various factors aside from statutory holidays may result in RT not being delivered on a day that otherwise could be a potential RT treatment day. It is expected that sites will attempt to keep the overall RT treatment duration as close to 7 weeks as possible, but inability to deliver the RT fraction to a patient on a given day is not a PD unless >2 consecutive regular treatment days (Mon-Fri) are missed. Sites are encouraged to consider BID treatments, at least 6 hours apart, for making up missed RT fractions to maintain the overall treatment time.

RT delivered to the total dose of 70 Gy is a completed dose, regardless of delays in RT delivery.

#### **5.4.2. Cisplatin**

All patients will receive cisplatin (100 mg/m^2) administered IV on Days 1, 22, and 43 of the CRT Phase (note: cisplatin given within 48 hours of the scheduled days is acceptable). The actual dose of cisplatin administered should be based on actual body surface area (BSA).

In case of obesity (body mass index (BMI) >30 kg/m^2), actual BSA will still be used according to the ASCO recommendation published in the Journal of Clinical Oncology, 2012: Appropriate Chemotherapy Dosing for Obese Patients with Cancer ([Appendix 8](#)).

Cisplatin is to be given on a Q3W schedule of 100 mg/m^2 (a weekly dosing schedule is not allowed on protocol) on Day 1, 22 and 43 of the CRT phase. The 100 mg/m^2 dose may be split over 2 to 4 consecutive days (eg, 50 mg/m^2 on 2 consecutive days up to 25 mg/m^2 over 4 consecutive days) if that is the institutional standard way of delivering the Q3W cisplatin dosing. It is recognized that some patients will not be able to receive the 3rd dose of cisplatin and this is not a protocol deviation.

Complete information for cisplatin may be found in the SRSD, which for this study is the cisplatin package insert.

